Assessment calls will occur at Baseline and at 3, 6, 12, and 18 months after Baseline. The primary outcomes are abstinence from tobacco at the 18-month follow-up and abstinence across all follow-ups. Secondary outcomes are smoking quit attempts, cigarettes per day, use of the quitline, and cost-effectiveness. Participants will be scheduled to complete a baseline assessment call within one week. Following the baseline assessment, participants will be randomly assigned to ST or MAPS. Participants will schedule their first counseling call at that time (see Table 1).

Recruitment. Participants will be women with a diagnosis of cervical cancer or high grade cervical dysplasia who report smoking any cigarettes within the past 30 days, recruited through the Stephenson Cancer Center or OU Physicians at the University of Oklahoma Health Sciences Center, via the ClinicalTrials.gov website, by responding to recruitment flyers and internet advertisements (e.g., flyers in clinics, Facebook), and through referrals from healthcare providers.

Participant Eligibility. Inclusion criteria: ≥ 18 ; current smoker with a history of at least 100 lifetime cigarettes and a self-report of smoking within the last 30 days; history of cervical cancer or high grade cervical dysplasia (we have defined survivorship as beginning at the time of cancer diagnosis, consistent with the NCI definition); has a working cell phone; valid home address; speaks English, Spanish or both languages. Exclusion criteria: current use of tobacco cessation medications; self-report of being pregnant or lactating; or, another household member enrolled in the study; or contraindication of nicotine patch use unless under the supervision of a physician as advised by project staff.

Table 1. Schedule of Study Procedures and Assessments	Screening	Baseline	Month 3	Month 6	Month 12	Month 18
Inclusion/Exclusion Criteria	X	X				
Compensation		\$60	\$60	\$60	\$60	\$60
TREATMENT PROCEDURES						
Standard Treatment (ST)	Delivered at Baseline, and Months 6 and 12					
Motivation And Problem Solving (MAPS)	ST plus up to 6 MAPS Counseling Calls delivered over 12 months					
DEMOGRAPHICS, MENTAL HEALTH						
Demographics and Smoking History		X				
Cancer stage at diagnosis, time since diagnosis, current stage, treatment status	X					
Subjective Social Status		X	X	X	X	X
Fear of Cancer Recurrence Inventory (FCRI)	X	X	X	X	X	X
MOTIVATION						
Contemplation Ladder		X	X	X	X	X

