Baseline Assessment and Randomization. Eligible women who choose to participate will complete telephone-administered questionnaires where data are entered directly into a database. The system includes online error checking and is used in all of our ongoing research projects. After completing the assessment, participants will be randomly assigned to ST or MAPS using a form of adaptive randomization called minimization.^{100,101} Compared to techniques such as stratification, minimization results in better group balance with respect to participant characteristics. Minimization also provides for balanced treatment groups throughout the randomization process. Thus, for trials like this one that have extended accrual periods, the treatment groups remain balanced with respect to participant characteristics that may be related to time of accrual. In this study, we will randomize based on race/ethnicity, age, education, cigarettes/day, cervical cancer or dysplasia stage, cervical cancer or dysplasia treatment status, and time since diagnosis. After completing the assessment and randomization procedures, the 3-month follow-up assessment will be scheduled, and MAPS participants will schedule their first counseling call.

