Participants who self-report abstinence will be mailed a prepaid envelope, instructions for providing the cotinine sample, and a saliva cotinine kit. Research staff will contact participants by phone to ensure the arrival of packet, review the contents of the packet, and answer any questions participants may have about collecting a saliva specimen. Although cotinine cannot comprehensively validate the various abstinence definitions and timeframes, the most comprehensive review on biochemical validation concluded that misreporting is typically very low (~2%), and that adjustment for misreporting almost never influences analyses regarding relative treatment efficacy.¹⁰⁶ As such, our biochemical validation procedures are well justified both scientifically and practically.

PSYCHOLOGICAL DISTRESS ASSESSMENT AND MANAGEMENT PLAN

If a participant: 1) states that she is thinking about harming herself or others, or 2) uses actions or words to lead us to believe that she may be in eminent danger or in danger of harming another person, research staff will execute our standard crisis procedures. These procedures are described in detail in Appendix H. Once the plan is executed, a trained counselor will assess the participant using the "Crisis Assessment" (Appendix I). Participants will also be encouraged to follow ups with a mental health professional of their choice. Our team will have extensive interactions with participants throughout the course of the study. Therefore, our plan is appropriate for our target population.

STATISTICAL CONSIDERATIONS

Data Analysis Approach. The primary outcome is abstinence from smoking at the 18-month assessment. To test the treatment effect at 18 months, we will conduct logistic regression analysis with abstinence as the outcome variable, and treatment (a two-level categorical variable) as the predictor, adjusting for covariates, specifically, factors used in the minimization procedures (race/ethnicity, language, age, education, income, cigarettes/day, cervical cancer stage, and time since diagnosis). Interactions between treatment and specific covariates of interest may be included and tested for exploratory purposes.

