Because the primary and secondary outcomes and mechanisms include repeated measurements that are correlated within subjects, our data analytic approach will also utilize generalized linear mixed model regression (GLMM)^{107,108} to analyze the effects of MAPS across the 3, 6, 12, and 18 month timepoints. For abstinence, we will assume a logit link and binomial variance function for the GLMM, and parameterize them with blocking on individual nested within treatment conditions. Treatment and time will be included, as well as their interaction, with adjustment for relevant covariates. The effects of interactions between treatment and specific covariates will also be examined. Similarly analyses will also be conducted to assess the MAPS effects on quit attempt and use of the quitline (both binary). To assess MAPS effects on continuous measures such as cigarettes per day and mechanisms, the GLMM analysis will be replaced by linear mixed model (LMM) analysis (i.e., a special case of the GLMM). Similarly, the logistic regression analysis for the 18-month assessment will be replaced by multiple linear regression. Normalizing transformations for continuous measures (such as cigarettes per day) will be applied as appropriate. Alternatively, Poisson GLMM or Poisson regression could be used to analyze the effect of MAPS on cigarettes per day. In addition to examining the effects of treatment on primary and secondary outcomes and mechanisms, we will also assess the mediation (indirect) effects of treatment on abstinence through the mechanisms (motivation, agency, stress/negative affect) using single and/or multiple mediator models.¹⁰⁹ With the primary outcome being abstinence at the 18-month assessment, potential mediators will be mechanisms measured at the previous time points (i.e., 3, 6, and 12 months), one at a time. A recommended approach to estimating and/or testing for the indirect effects for a binary outcome variable is via coefficient standardization in the *b* path (e.g., logistic regression), as appropriate, and bootstrapping.¹⁰⁹⁻¹¹¹ Appropriate covariates including mediators measured as baseline will be

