Power. Our power analysis is based primarily on the comparison of 18-month abstinence rates between MAPS and ST. Because an intent-to-treat approach will be used, power is calculated based on the full sample without attrition (N=300; 150 per group), given that individuals lost to follow-up will be treated as smoking). All power analyses assume a significance level of 0.05 and a two-sided test. Based on the *Guideline*,²⁰ we estimated that abstinence for ST would be approximately 10%. Using a chi-square test to examine the effect of treatment on abstinence at 18 months, a sample size of 300 (150 per group) will provide 80% power to detect an overall treatment effect that corresponds to abstinence rates of 10% and 21.9% in ST and MAPS respectively. Relative to examining abstinence over time, these calculations represent the worst case scenario. Table 2 presents detectable differences across a range of possible abstinence rates. Analyses conducted using GLMM will have greater power to detect the same average differences across time.

Table 2. Detectable differences in binary smoking outcomes with 80% power (abstinence, quit attempt)	
ST (n=150)	MAPS (n=150)
5.0%	14.60%
10.0%	21.90%
20.0%	34.40%
30.0%	45.70%
40.0%	56.20%

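### The covariates the primary model calls minimization factors are not the factors the randomization section names: language and income appear only in the model, treatment status only in the randomization

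*Combined protocol and SAP*

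**What the plan says.** Under Baseline Assessment and Randomization, women are "randomly assigned to ST or MAPS using a form of adaptive randomization called minimization", and the section commits to seven factors: "we will randomize based on race/ethnicity, age, education, cigarettes/day, cervical cancer or dysplasia stage, cervical cancer or dysplasia treatment status, and time since diagnosis".

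Under Statistical Considerations, Data Analysis Approach, "The primary outcome is abstinence from smoking at the 18-month assessment". It is tested by logistic regression on treatment with covariate adjustment, and the covariates are specified as "factors used in the minimization procedures (race/ethnicity, language, age, education, income, cigarettes/day, cervical cancer stage, and time since diagnosis". That list has eight items.

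Three other places touch on the subject:

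- Table 1 has a screening row, "Cancer stage at diagnosis, time since diagnosis, current stage, treatment status", so treatment status is known before allocation.
- The repeated-measures model is described only in general terms: "Treatment and time will be included, as well as their interaction, with adjustment for relevant covariates".
- The Power section uses no covariates: "Using a chi-square test to examine the effect of treatment on abstinence at 18 months".

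**The concern.** The plan's rule is to adjust the primary test for whatever was balanced in the allocation. That is the usual practice after minimization, but it works only if the list in the model is the list in the algorithm. Here the model's list is presented as the minimization factors themselves, not as those factors plus some extra covariates. Even if language and income were read as extras, that would not explain why treatment status is missing.

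One of two things is therefore true. If the randomization section describes what was done, the primary model breaks its own rule by leaving out a balancing factor. If the analysis section is right, the randomization section misdescribes the allocation. Either way, an analyst could follow the label (the factors actually minimized on) or the printed list, and the two can give different answers. Pre-specifying the single primary test is meant to remove that choice.

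**Working it through.** **1. The two lists side by side**

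| Factor | Randomization section | Primary model |
|---|---|---|
| Race/ethnicity | yes | yes |
| Age | yes | yes |
| Education | yes | yes |
| Cigarettes/day | yes | yes |
| Stage | yes (cancer or dysplasia) | yes (cancer only, as worded) |
| Time since diagnosis | yes | yes |
| Treatment status | yes | no |
| Language | no | yes |
| Income | no | yes |

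The randomization section has 7 factors and the model has 8, with 6 in common. That leaves 7 − 6 = 1 only in the randomization (treatment status) and 8 − 6 = 2 only in the model (language and income). Stage is counted as a match by treating the model's wording as shorthand. Taken literally it would not cover women with high grade dysplasia, who are eligible.

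**2. Does another section settle it?** No. The repeated-measures text does not name its covariates, and the Power section has none. Both conflicting sentences are complete, current text of the same protocol version.

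**3. The plan's own power figure.** Inputs from the Power section: n = 150 per group, p1 = 0.10, p2 = 0.219, two-sided alpha 0.05. The mean rate p̄ is 0.1595.

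Power = Φ{[(p2 − p1) − 1.96·√(2p̄(1 − p̄)/n)] / √([p1(1 − p1) + p2(1 − p2)]/n)}

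- 1.96·√(0.26812/150) = 1.96 × 0.04228 = 0.0829
- √((0.0900 + 0.1710)/150) = 0.0417
- (0.119 − 0.0829)/0.0417 = 0.866, and Φ(0.866) = 0.807

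This agrees with the stated 80%. No covariates enter, so correcting the list changes no stated figure.

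**4. How much could the mismatch matter?** The documents give no covariate-outcome associations, so this step is assumption-based. The set-up was:

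- 300 women, minimized with a 0.8 biased coin on the seven factors of the randomization section.
- All factors binary, with prevalence 50% except treatment status (30%) and language (20%).
- Odds ratios for abstinence of 1, 2 or 4 for treatment status, 1.5 or 2 for language and income, and 1.5 for the other factors.
- Treatment status either independent of stage and time since diagnosis, or correlated with them at about 0.38 in size.
- Logistic Wald test at two-sided 0.05.
- Per scenario, 30,000 null trials (10% in both arms) and 20,000 trials at 10% vs 21.9%.

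The Monte Carlo standard error of the type I error is √(0.05 × 0.95/30,000) = 0.13 percentage point. Each range below covers the four combinations of correlation and language/income odds ratio.

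| Treatment-status odds ratio | Type I, model's list | Type I, model's list plus treatment status | Power, model's list | Power, model's list plus treatment status |
|---|---|---|---|---|
| 1 | 4.87–5.09% | 4.93–5.18% | 82.6–83.1% | 82.7–83.1% |
| 2 | 4.88–5.04% | 5.03–5.25% | 82.6–83.8% | 82.9–84.2% |
| 4 | 4.47–4.60% | 5.04–5.17% | 82.8–84.0% | 84.6–85.3% |

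- Within scenarios, adding treatment status to the model's list changes power by +0.0 to +1.9 points.
- Power with the randomization section's list minus power with the model's list runs from −0.9 to +1.6 points, so neither list is uniformly better.
- The two lists disagree on significance at 0.05 in 1.2% to 2.0% of null trials and 2.5% to 4.3% of trials at the design effect.
- Shorter repeats of the independent-factor case, with separately written code, agreed in direction and size. The largest power gain seen in any of them was about 2.5 points.

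**The case against.** The strongest reply is that this is an editorial slip with no practical effect. The model names its outcome, its form and eight covariates, so it can be fitted exactly as written. Its type I error does not exceed 5% by more than simulation noise, and stated power is untouched. The simulation inputs are all assumed: the document gives no prevalences, correlations, factor levels, coin probability or effect sizes. The only clear departure from 5% is mild conservatism at a treatment-status odds ratio of 4, for which the document offers no basis. In a variant with several three- and four-level factors (3,000 trials per scenario, standard error about 0.4 point), type I error with the model's list was 5.1% to 5.3%, and adding treatment status moved power by only +0.3 to +0.8 point. The conservatism did not reappear, though that run was too small to exclude it.

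There is also a sparseness point. The design rates imply 150 × 0.10 + 150 × 0.219 = 15 + 32.85, or about 48 abstainers, and 30 if both arms are at 10%. In the multi-level variant, 9% to 11% of null fits had a very large coefficient under every list, and treatment status added at most 1.5 points to that.

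Most of this stands as a limit on size. The effect is small, and the mild conservatism should not be presented as a general result. Coding of sparse categories matters whichever list is used. None of it reconciles the two sections. That the printed list can be fitted does not make it the list of minimization factors.

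**Conclusion.** The contradiction is certain from the text: three factors differ, and at most one of the two sections describes the minimization correctly. The document does not show which.

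The statistical consequence is minor and cannot be sized from the document alone. Under the assumed effects there is no meaningful type I inflation, possibly slight conservatism if treatment status is strongly prognostic, and a power change of no more than about 2.5 points in any run. The two lists would reach different conclusions in a few percent of trials at most. The 80% power claim is unaffected.

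This should be corrected, but it does not threaten the trial's validity. The reason to act is that the covariate set of the single primary test should demonstrably match the allocation, and making it match is nearly free.

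**What to change.** Before unblinded analysis:

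1. Read the factors from the implemented minimization algorithm.
2. Correct whichever section is wrong, so that both carry the same list.
3. Adjust the primary model for every factor actually used.

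If the randomization section is right, add treatment status to the model. Language and income may stay as pre-specified additional baseline covariates, but should not be labelled minimization factors. If the analysis section is right, correct the list in the randomization section. In either case, word the stage factor in the model so that it covers dysplasia as well as cancer, as the randomization section does. With about 48 abstainers expected, it would also help to state how multi-level factors are categorised in the model.

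The cost is one look at the minimization settings and an edit to one or two sentences. No new data are needed for treatment status, because Table 1 already records it at screening.

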Assessments. Research Electronic Data Capture (REDCap) will be used to administer all questionnaires over the phone, in person, and/or via a web-based link when convenient for the participant. REDCap is a secure, web-based application designed to support data capture and utilizes a computer-administered self-interview format. This system is used in all of our current research and is designed to comply with all HIPAA regulations. Having research staff read the questionnaire items to participants will help overcome problems related to low literacy levels. Finally, we will attempt to reduce the inconvenience associated with completing assessments by providing financial compensation for participants' time. In sum, the battery of instruments comprehensively assesses our hypothesized mechanisms and associated variables of interest. A copy of each assessment instrument is included in the Appendix and all measures are listed in the Procedures Table (Table 1).

Smoking Abstinence. Abstinence assessments are based on recommendations from the Society for Research on Nicotine and Tobacco (SRNT).¹⁰⁵ We will report both prolonged and point-prevalence abstinence

at all follow-up assessment points. Prolonged abstinence refers to abstinence beginning with the initiation of treatment and including a grace period. The prolonged abstinence measure utilizes SRNT's recommendation for determining relapse (i.e., 7 consecutive days of smoking or smoking in each of 2 consecutive weeks). We will also evaluate two point-prevalence abstinence measures: 1) no smoking during the previous 7 days, and 2) no smoking during the previous 30 days. For all abstinence measures, we will analyze both completers only, and intent to treat in which smokers lost to follow-up are considered smoking. Abstinence at all follow-ups will be biochemically verified using a saliva cotinine level of <20 ng/ml.

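### On its natural reading, the repeated-measures GLMM gives no stable odds ratio for prolonged abstinence and, for point prevalence, an odds ratio that is not the population effect; the estimand and estimation method should be stated

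*Combined protocol and SAP*

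**What the plan says.** The Data Analysis Approach tests 18-month abstinence by ordinary logistic regression. It adds a generalized linear mixed model "to analyze the effects of MAPS across the 3, 6, 12, and 18 month timepoints". For abstinence the plan will "assume a logit link and binomial variance function for the GLMM, and parameterize them with blocking on individual nested within treatment conditions". On the fixed effects: "Treatment and time will be included, as well as their interaction, with adjustment for relevant covariates". No random-effects distribution, estimation method or averaging contrast is given.

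The Smoking Abstinence section says "We will report both prolonged and point-prevalence abstinence" at every follow-up. Prolonged abstinence runs from the start of treatment, after a grace period of unstated length, and ends by a relapse rule. Point prevalence has a 7-day and a 30-day version. Each measure is analysed in completers and with women lost to follow-up counted as smokers. Neither section says which measure the GLMM uses.

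The Power section says of the repeated-measures analysis: "Analyses conducted using GLMM will have greater power to detect the same average differences across time".

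The status of that analysis differs by section. Project Design and Procedures lists abstinence over all follow-ups as a primary outcome beside month 18. The Specific Aims and the Data Analysis Approach name month 18 alone.

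**The concern.** A logit mixed model with the individual as block is ordinarily a random-intercept model. Two consequences follow on that reading.

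First, a woman who has relapsed cannot be prolonged-abstinent at a later visit. Apart from missed or unverified visits, only the patterns 1111, 1110, 1100, 1000 and 0000 can occur. Such data push the random-intercept variance towards infinity, and the treatment odds ratio goes with it.

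Second, for point prevalence the coefficient compares the odds for women with the same random intercept. It is not the contrast between arm-level rates on which the power calculation, the 18-month test and the count of quitters in the cost-effectiveness analysis rest.

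At stake is a result printed beside the 18-month odds ratio on a scale that cannot be compared with it, for an outcome that one section calls primary. For prolonged abstinence, the printed number would depend largely on the fitting method and the coding of missed visits.

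**Working it through.** **Inputs from the Power section.** "All power analyses assume a significance level of 0.05 and a two-sided test". Also, "power is calculated based on the full sample without attrition (N=300; 150 per group", and the target is "80% power to detect an overall treatment effect that corresponds to abstinence rates of 10% and 21.9% in ST and MAPS respectively".

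**Plan's own figure.** Chi-square test without continuity correction, 150 per arm, mean rate (0.10 + 0.219)/2 = 0.1595:

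z = [0.119·√150 − 1.96·√(2·0.1595·0.8405)] / √(0.10·0.90 + 0.219·0.781) = (1.457 − 1.015)/0.511 = 0.866, so power = 80.7%. The stated 80% is reproduced.

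**Population odds ratio.** (0.219/0.781)/(0.10/0.90) = 2.52.

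**Point prevalence.** Under a normal random intercept with standard deviation σ, the rate in an arm is the average of 1/(1 + exp(−(a + σZ))) over a standard normal Z. Solve for a in each arm so that the rates stay at 10% and 21.9%. At σ = 2, a = −3.417 and −2.052, so the subject-specific odds ratio is exp(1.365) = 3.92. For other values:

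| σ (assumed) | 1 | 2 | 3 | 4 | 5 |
|---|---|---|---|---|---|
| Odds ratio | 2.85 | 3.92 | 5.89 | 9.23 | 14.75 |

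The documents give no within-woman correlation. Random-intercept maximum-likelihood fits to expected four-visit patterns from a latent normal model, with 10% and 21.9% abstinent at every visit, give:

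| Latent correlation (assumed; lag 1 for AR(1)) | 0.3 | 0.5 | 0.7 | 0.8 | 0.9 |
|---|---|---|---|---|---|
| Exchangeable | 2.98 | 3.62 | 5.25 | 7.60 | 17.5 |
| AR(1) | 2.77 | 3.15 | 4.12 | 5.45 | 10.4 |

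Every entry describes the same 10% and 21.9%.

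**Prolonged abstinence, strictly monotone.** Assumed rates at months 3, 6, 12 and 18: ST 18/15/12/10%, MAPS 34/30/26/21.9%. Maximised log-likelihood at fixed σ (saturated value −251.54):

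| σ | 2 | 4 | 10 | 20 | 40 | 80 |
|---|---|---|---|---|---|---|
| Log-likelihood | −363.2 | −299.0 | −263.0 | −254.1 | −251.77 | −251.54 |
| Month-18 odds ratio | 4.5 | 11 | 204 | 29,000 | 6.5×10⁸ | 4×10¹⁷ |

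The likelihood keeps rising towards its bound, so there is no finite maximum. A hand check on the growth: for large σ each arm's rate is set by a normal threshold, so log(odds ratio)/σ should approach Φ⁻¹(0.219) − Φ⁻¹(0.10) = −0.776 + 1.282 = 0.506. The table's unrounded values give 0.514, 0.507 and 0.506 at σ = 20, 40 and 80.

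**The same outcome under other choices.**

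- Intermittent missed visits coded as smoking, visit by visit. This breaks the monotone pattern, and the best σ on the grid is finite:

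| Missing per visit (assumed) | 2% | 5% | 10% | 20% |
|---|---|---|---|---|
| Best σ on the grid | 15 | 10 | 8 | 5 |
| Month-18 odds ratio | about 2,340 | 183 | 62 | 14 |

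- Penalised quasi-likelihood (PQL) on the strictly monotone data: σ = 2.56, month-18 odds ratio 3.65.
- GEE with exchangeable correlation on the strictly monotone data: 2.35, 2.49, 2.58 and 2.54 at the four visits. The last is close to the planned 2.52.

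**Effect on the test.** In a simulation of point prevalence with 150 per arm, four visits, exchangeable latent correlation 0.6 and 0.8, and 150 replicates each, power was 97% and 97% for the random-intercept likelihood-ratio test against 97% and 95% for GEE. Null rejection was 1% and 4% against 1% and 5%. Median GLMM odds ratios were 4.3 and 7.8. The replicates are few, but the decisions barely differ.

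**The case against.** The plan never mentions a random intercept. Its wording, including the binomial variance function, also fits a residual-side (marginal) block covariance, under which neither problem arises. This stands: the random intercept is the natural reading of a mixed model blocked on individual, not stated text.

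Nor does the plan say that prolonged abstinence will enter the GLMM. It says that the measure will be reported at each follow-up. This stands too, but the model is written for abstinence without qualification, and nothing excludes the prolonged measure.

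Divergence needs full maximum likelihood and strictly monotone patterns. Counting lost women as smokers, or an unreturned cotinine kit, can produce a 0 followed by a 1, and PQL converges anyway. This is correct, but it does not rescue the analysis: the answer then ranges from 3.65 to about 2,340 according to choices that the plan leaves open.

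A reader might infer that the GLMM inflates the effect of MAPS several-fold. The documents do not support that. A subject-specific odds ratio is a valid answer to a different question, its size rests on a correlation that they do not give, and the test is hardly altered.

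Finally, including a treatment-by-time term does not mean that the raw treatment coefficient will be reported. Averaged contrasts are routine from such a model; the plan simply names none.

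**Conclusion.** The point holds as a gap in specification with real consequences, conditional on the random-intercept reading. For strictly monotone prolonged abstinence, maximum likelihood has no finite treatment odds ratio. Other fitting or coding choices give about 3.7 (PQL), or 14 to 2,300 at assumed intermittent missingness of 20% to 2%. For point prevalence, the coefficient exceeds 2.52 and lies at about 2.8 to 17 for assumed latent correlations of 0.3 to 0.9. It does not express the average difference across time that the Power section names, and it cannot be set beside the 18-month odds ratio.

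It would go too far to say that the trial's main result is compromised. The 18-month logistic regression, its power calculation and the 18-month count of quitters do not use the GLMM. The point has weight because Project Design and Procedures lists abstinence across follow-ups as primary, although the Specific Aims and the Data Analysis Approach do not. Should-fix, moderate confidence.

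**What to change.** - State in the Data Analysis Approach which abstinence measure enters the repeated-measures model, whether the block is a random intercept or a marginal covariance, and the estimation method.
- For repeated point-prevalence abstinence, report arm-level abstinence rates standardised from the GLMM. Give the equal-weight average difference over months 3, 6, 12 and 18 with its confidence interval. GEE on the missing-as-smoking and multiply imputed data is an acceptable alternative; replacing the GLMM is optional.
- Do not fit the random-intercept GLMM to prolonged abstinence. Analyse it visit by visit with the logistic model already planned for month 18, or with a marginal model.

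The cost is SAP wording and slightly more analysis work in standard software. The drawback of GEE is that completers-only data would have to be missing completely at random, whereas a correctly specified mixed model is valid under missing at random. For that analysis, standardised GLMM rates are the better choice.
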